#### 3.5.2 Secondary Efficacy Endpoints and Analyses

The protocol defined 6 secondary efficacy endpoints. Endpoints 1, 2, and 3 are key secondary endpoints to be considered for study-wise Type I error control:

- 1. Annualized flare rate for treated and AC-determined IgG4-RD flares during the RCP.
- 2. The proportion of subjects achieving flare-free, treatment-free complete remission at Week 52,
- 3. The proportion of subjects achieving flare-free, corticosteroid-free complete remission at Week 52.
- 4. Time to initiation of first treatment (medication or procedure) for new or worsening disease activity by the Investigator within the RCP, regardless of AC determination of flare.
- 5. Annualized flare rate for AC-determined IgG4-RD flares, whether or not treated, during the RCP.
- 6. Glucocorticoid (GC) use, calculated as the cumulative GC dose taken for the purpose of IgG4-RD disease control during the RCP.
- 3.5.2.1 Annualized Flare Rate for treated and AC-determined IgG4-RD Flares During the RCP

The estimand with a treatment policy strategy is defined by the following:

• Target population: Subjects in the FAS

- Variable: The number of treated AC-determined IgG4-RD flares experienced during 52-week RCP
- Intercurrent event: No intercurrent events will be taken into account. All data captured during the 52-week RCP will be used for analysis.
- Population-level summary: Rate ratio between inebilizumab versus placebo and its associated 95% CI.

The number of treated and AC-determined flares will be compared between the inebilizumab group and the placebo group using a negative binomial model. The model will include covariates of treatment group (inebilizumab or placebo) and stratification factors. The logarithm of the subject's corresponding follow-up time will be used as an offset variable in the model to adjust for subjects having different exposure times during which the events occur. The estimated treatment effect (ie, the rate ratio of inebilizumab versus placebo), corresponding 95% CI, and two-sided p-value for the rate ratio will be presented.

In addition, the annualized flare rate and the corresponding 95% CI within each treatment group, and the absolute difference between treatment groups with the corresponding 95% CI, will be presented.

An additional analysis may be conducted by considering subjects, who receive 1) any treatment for IgG4-RD, including GC or immunosuppressive treatment (other than GC tapered in accordance with the protocol-specified schedule during the first 8 weeks of the RCP) and/or 2) any prohibited GC or immunosuppressive treatment, to be censored at the time when relevant treatment was first received.

3.5.2.2 The Proportion of Subjects Achieving Flare-Free, Treatment-Free Complete Remission at Week 52

Flare-free, treatment-free complete remission is defined as lack of evident disease activity at Week 52, no AC-determined flare during the RCP, and no treatment for flare or disease control except the required 8-week GC taper. Lack of evident disease activity is defined as either an IgG4- RD Responder Index (Wallace et al, 2018) score of 0, or a determination by the investigator that no disease activity is present based on physical, laboratory, pathology or other evidence.

The estimand with a composite strategy is defined by the following:

- Target population: Subjects in the FAS
- Variable: Proportion of subjects achieving flare-free, treatment-free complete remission at Week 52
- Intercurrent event: Subjects who receive treatment for flare or disease control except the required 8-week GC taper will be treated as not achieving complete remission at Week 52.
- Population-level summary: Odds ratio between inebilizumab versus placebo and its associated 95% CI.

The results of the analyses will be presented using odds ratios, together with associated 95% CI and two-sided p-value. In addition, the absolute difference of the proportions between treatment groups with the corresponding 95% CI and two-sided p-value, will also be presented.

The estimate of the treatment effect will be assessed using a logistic regression model. The response variable in the model will be whether or not a subject achieves the corresponding flare-free treatment-free complete remission at Week 52. The model will have treatment indicator (inebilizumab or placebo) and stratification factor as the explanatory variables. SAS PROC LOGISTIC and PROC GENMOD with LOGIT link will be used for fitting this model and estimate odds ratio and absolute difference of the proportions, respectively.

An additional analysis under a treatment policy strategy with the same model will be conducted, with complete remission defined as an IgG4-RD RI score of 0 at Week 52, no AC-determined flare, and no treatment for flare except the required 8-week GC taper during the RCP.

For both analyses, subjects who do not complete the RCP or are missing IgG4-RD disease activity assessment at Week 52 will be treated as not achieving complete remission at Week 52.

3.5.2.3 The Proportion of Subjects Achieving Flare-Free, Corticosteroid-Free Complete Remission at Week 52

Flare-free, corticosteroid-free complete remission is defined as lack of evident disease activity at Week 52, no AC-determined flare during the RCP, and no corticosteroid treatment for flare or disease control except the required 8-week GC taper. Lack of evident disease activity is defined as either an IgG4- RD Responder Index (Wallace et al, 2018) score of 0, or a determination by the investigator that no disease activity is present based on physical, laboratory, pathology or other evidence.

The estimand with a composite strategy is defined by the following:

- Target population: Subjects in the FAS
- Variable: Proportion of subjects achieving flare-free, corticosteroid-free complete remission at Week 52
- Intercurrent event: Subjects who receive corticosteroid for flare or disease control except the required 8-week GC taper will be treated as not achieving complete remission at Week 52.
- Population-level summary: Odds ratio between inebilizumab versus placebo and its associated 95% CI.

The results of the analyses will be presented using odds ratios, together with associated 95% CI and two-sided p-value. In addition, the absolute difference of the proportions between treatment groups with the corresponding 95% CI and two-sided p-value, will also be presented.

The estimate of the treatment effect will be assessed using a logistic regression model. The response variable in the model will be whether or not a subject achieves the corresponding flare-free corticosteroid-free complete remission at Week 52. The model will have treatment indicator (inebilizumab or placebo) and stratification factor as the explanatory variables. SAS PROC LOGISTIC and PROC GENMOD with LOGIT link will be used for fitting this model and estimate odds ratio and absolute difference of the proportions, respectively.

For both analyses, subjects who do not complete the RCP or are missing IgG4-RD disease activity assessment at Week 52 will be treated as not achieving complete remission at Week 52.

3.5.2.4 Time to Initiation of First Treatment for New or Worsening Disease Activity by the Investigator Within the RCP, Regardless of AC Determination of Flare

The estimand with a treatment policy strategy is defined by the following:

- Target population: Subjects in the FAS
- Variable: Time in days from Day 1 (dosing) to the date of the first treatment (new or increased GC treatment, other immunotherapy, or interventional procedure) for new or worsening disease activity by the investigator within the RCP, regardless of AC determination of flare within the 52-week RCP
- Intercurrent event: All data captured during the 52-week RCP will be used for analysis. Subjects who do not complete the RCP and have not received treatment for new or worsening disease activity as defined above, will be censored at the time of discontinuation.
- Population-level summary: HR between inebilizumab versus placebo and its associated 95% CI.

The hazard rate in the inebilizumab group will be compared to that in the placebo group using the Cox proportional hazards model with the treatment indicator (inebilizumab or placebo) and the stratification factor as the explanatory variables. The HR of inebilizumab versus placebo will be estimated together with its associated 95% CI.

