Section 9.3 Determination of Sample Size	Added text to clarify the rationale for the blinded event rate assessment and to indicate that this analysis "may" take place rather that "will" take place	Clarification of the purpose of the blinded event assessment, and description as optional.
Section 9.5.5 Safety Analysis	Added summary for SFUP	To be consistent to the change of the safety follow up period

Protocol Amendment 9 (Global) (15JUN2023)

Protocol Section(s) Impacted by Change	Change	Reason for Change
Title page	Updated name and address of Sponsor	Acquisition of Viela Bio by Horizon Therapeutics
Synopsis; Section 3.2 Secondary Objectives and Endpoints; Section 9.5.2.3 Flare-free Complete Remission; Section 9.5.3 Control of Type I Error	Updated definition of flare-free complete remission to include either a Responder Index score of 0, or determination by the investigator that there is no active disease, at the Week 52 visit	Expanded definition avoids subjects without active disease failing to meet this endpoint due to requirement for a Responder Index score of 2 in the absence of imaging
Section 6.1.2. Availability of Laboratory Results	Specified that serum Ig results will be made available beginning at OLP Week 26	Numerous requests from investigators for access to this data to monitor patient safety (e.g., risk of infection). At this point in the OLP, the risk of serum Ig results unmasking treatment assignment in the preceding RCP is very low.
Section 6.2.2 Schedule of RCP Assessments and Procedures	Footnote 'd' to Table 4 was updated	Clarification due to elimination of 90 day follow-up at the last protocol amendment (replaced by 2 year Safety Follow-Up)
Section 6.2.3 Schedule of OLP Assessments	Vital sign assessments for dosing visits in years 2-3 of the OLP denoted with superscript 'd'	Unintentionally omitted in previous amendment
Section 6.2.4 Safety Follow-Up Period	Visit windows added to Table 6	Unintentionally omitted in previous amendment
Section 6.3.3.3 Pregnancy; Section 8.3 Reporting Adverse Events; Section 8.4 Adverse Events of Special Interest; Section 8.5.1 Pregnancy; Section 8.5.2 Overdose or Misuse	Updated "ICON" to "Sponsor"; updated safety reporting email and fax numbers	Change from ICON to internal safety reporting process

Protocol Section(s) Impacted by Change	Change	Reason for Change
All	Typographical and formatting corrections	n/a

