9.5.2 Analysis of Secondary Efficacy Endpoints

9.5.2.1 Annualized Flare Rate for Treated and AC-determined Flares During the RCP

The annualized flare rate for treated and AC-determined flares during the RCP will be analyzed with a treatment policy strategy, which includes all data captured during the 52-week RCP. The efficacy variable is annualized flare rate, which will be compared between the inebilizumab group and the placebo group using a negative binomial model. The response variable in the model will be the number of treated AC-determined flares experienced by a subject over the 52-week RCP. The model will include covariates of treatment group (inebilizumab or placebo) and stratification factor. The logarithm of the subject's corresponding follow-up time will be used as an offset variable in the model to adjust for patients having different exposure times during which the events occur.

The estimated treatment effect (ie, the rate ratio of inebilizumab versus placebo), corresponding 95% CI, and two-sided p-value for the rate ratio will be presented. In addition, the annual flare rate and the corresponding 95% CI within each treatment group, and the absolute difference between treatment groups with the corresponding 95% CI, will be presented.

9.5.2.2 Annualized Flare Rate for AC-determined Flares During the RCP, Whether or Not Treated

The annualized flare rate for AC-determined flares, whether or not treated, during the RCP will be analyzed with a treatment policy strategy, which includes all data captured during the 52-week RCP. The efficacy variable is the annualized flare rate, which will be compared between the inebilizumab group and the placebo group using a negative binomial model. The response variable in the model will be the number of AC-determined flares, regardless of treatment experienced by a subject, over the 52-week RCP. The model will include covariates of treatment group (inebilizumab or placebo) and stratification factor. The logarithm of the subject's corresponding follow-up time will be used as an offset variable in the model to adjust for patients having different exposure times during which the events occur.

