9.5.2.3 Flare-free Treatment-free Complete Remission

Two types of flare-free complete remission will be analyzed: flare-free treatment-free complete remission and flare-free corticosteroid-free complete remission.

Flare-free treatment-free complete remission is defined as the lack of evident disease activity at Week 52, no AC-determined flare during the RCP, and no treatment for flare or disease control during the RCP except the required 8-week GC taper. Lack of evident disease activity is defined as either an IgG4-RD Responder Index (Wallace) score of 0, or a determination by the investigator that no disease activity is present based on physical, laboratory, pathology or other evidence.

Flare-free corticosteroid-free complete remission is defined as the lack of evident disease activity at Week 52, no AC-determined flare during the RCP, and no corticosteroid treatment for flare or disease control during the RCP except the required 8-week GC taper. Lack of evident disease activity is defined as either an IgG4-RD Responder Index (Wallace) score of 0, or a determination by the investigator that no disease activity is present based on physical, laboratory, pathology or other evidence.

The analysis of the proportion of subjects achieving each flare-free complete remission defined above for the composite estimand will include all data captured during the 52-week RCP. For both of these endpoints, the efficacy variable for each flare-free complete remission is the proportion of subjects achieving the corresponding flare-free complete remission at Week 52, which will be assessed using a logistic regression model respectively. The response variable in the model will be whether or not a subject achieves the corresponding flare-free complete remission at Week 52. The model will have treatment indicator (inebilizumab or placebo) and stratification factor as the explanatory variables.

Subjects who discontinue prematurely from the RCP will be treated as not achieving complete remission at Week 52. The results of the analyses will be presented using odds ratios, together with associated 95% CI and two-sided p-value for inebilizumab versus placebo.

An additional analysis under a treatment policy strategy with the same model will be conducted, with complete remission defined as the lack of evident disease activity at Week 52 and no AC-determined flare during the RCP.

9.5.2.4 Time to Initiation of Treatment for IgG4-RD, Regardless of AC Determination of Flare

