# 3.5.2.5 Annualized Flare Rate for AC-Determined IgG4-RD Flares, Whether or not Treated, During the RCP

The estimand with a treatment policy strategy is defined by the following:

- Target population: Subjects in the FAS
- Variable: The number of AC-determined IgG4-RD flares, whether or not treated, experienced during 52-week RCP
- Intercurrent event: No intercurrent events will be taken into account. All data captured during the 52-week RCP will be used for analysis.
- Population-level summary: Rate ratio between inebilizumab versus placebo and its associated 95% CI.

The number of treated AC-determined flares will be compared between the inebilizumab group and the placebo group using a negative binomial model. The model will include covariates of treatment group (inebilizumab or placebo) and stratification factors. The logarithm of the subject's corresponding follow-up time will be used as an offset variable in the model to adjust for subjects having different exposure times during which the events occur. The estimated treatment effect (ie, the rate ratio of inebilizumab versus placebo), corresponding 95% CI, and two-sided p-value for the rate ratio will be presented.

In addition, the annualized flare rate and the corresponding 95% CI within each treatment group, and the absolute difference between treatment groups with the corresponding 95% CI, will be presented.

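### The SAP's additional treatment-policy remission analysis still fails subjects treated for flare and accepts only RI = 0, contrary to the protocol; one model sentence in SAP 3.5.2.5 also wrongly restricts to treated flares

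*SAP*

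**What the plan says.** **Remission.** Protocol 9.5.2.3 defines the main remission endpoints as composites in which treatment counts as failure. It then adds a treatment-policy analysis using the same logistic model, "with complete remission defined as the lack of evident disease activity at Week 52 and no AC-determined flare during the RCP". That section lets lack of evident activity be met by RI = 0 or by the investigator's determination.

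SAP 3.5.2.2 keeps the composite for the main analysis: "Subjects who receive treatment for flare or disease control except the required 8-week GC taper will be treated as not achieving complete remission". It then states "An additional analysis under a treatment policy strategy with the same model will be conducted". The definition that the SAP attaches to this second analysis is "complete remission defined as an IgG4-RD RI score of 0 at Week 52, no AC-determined flare, and no treatment for flare", the required 8-week taper excepted.

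The Amendment 9 entry in the protocol's summary of changes gives the reason for the either/or activity criterion: "Expanded definition avoids subjects without active disease failing to meet this endpoint due to requirement for a Responder Index score of 2" when there is no imaging. It is cited here only for that reason.

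**Flare rate.** SAP 3.5.2.5 concerns AC-determined flares irrespective of treatment. Its estimand variable is "The number of AC-determined IgG4-RD flares, whether or not treated, experienced during 52-week RCP", but its model sentence reads "The number of treated AC-determined flares will be compared between the inebilizumab group and the placebo group". Protocol 9.5.2.2 gives the response variable as "the number of AC-determined flares, regardless of treatment experienced by a subject, over the 52-week RCP".

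**The concern.** The additional remission analysis should answer one question: what happens to the treatment effect when treatment for IgG4-RD is no longer scored as failure? The protocol's version answers it, because it differs from the main composite only in dropping the treatment condition.

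The SAP's version differs in two ways at once. It relaxes the treatment condition only in part, since treatment for disease control no longer fails a subject but treatment for flare still does. It also tightens the activity criterion to RI = 0. A difference from the main result could come from either change, and agreement could come from the two cancelling.

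The subjects concerned are foreseeable. Protocol 6.3.2.1 lets the investigator treat whether or not flare criteria are met, so some completers may be treated for an event the AC does not confirm. Protocol 6.3.6 leaves imaging after randomization to the investigator, so the RI problem described in Amendment 9 can arise at Week 52.

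In SAP 3.5.2.5, programming the model sentence literally would repeat the count analysed for key secondary endpoint 1 and leave the intended endpoint unanalysed. Protocol 4.4 recognises flares that need no treatment, so the two counts can differ.

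**Working it through.** **Step 1: the three remission definitions side by side.** All require no AC-determined flare during the RCP. The SAP counts non-completers and subjects with a missing Week 52 assessment as failures in both of its analyses.

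| Analysis | Activity criterion | Treatment that counts as failure (taper excepted) |
|---|---|---|
| Main composite, SAP 3.5.2.2 | RI = 0 or investigator determination | For flare or disease control |
| Additional, Protocol 9.5.2.3 | RI = 0 or investigator determination | None |
| Additional, SAP 3.5.2.2 | RI = 0 only | For flare |

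Every main-composite responder is a responder under the protocol's additional definition, and the subjects gained are exactly those who had been failed for treatment alone. Every responder under the SAP's additional definition also meets the protocol's, but not the reverse. The SAP's additional definition and the main composite are not nested: each can count a responder whom the other fails.

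**Step 2: does the label allow this?** SAP 3.1 describes treatment policy as using all data captured during the RCP. Protocol 9.5.2.3 says the composite analysis also uses all RCP data, so data inclusion does not separate the two. What separates them is whether treatment is failure.

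**Step 3: illustration of size.** This compares the SAP's additional analysis with the protocol's.

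- From Protocol 9.3 and SAP 2.3: placebo flare probability 0.35; inebilizumab hazard 0.1508, so flare probability 1 - exp(-0.1508) = 0.14.
- Ceiling for remission under the protocol's additional definition: 1 - 0.35 = 0.65 and 1 - 0.14 = 0.86. This assumes no dropout, all flare-free subjects inactive, and no untreated AC-determined flares.
- SAP proportion = ceiling - a - b. Here a is the share treated for a flare the AC did not confirm, and b is the share inactive by investigator determination with RI > 0. No overlap is assumed. All values of a and b are assumptions; the documents give none.
- Odds ratio at the ceiling = (0.86/0.14)/(0.65/0.35) = 3.31.

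| a (placebo / inebilizumab) | b (placebo / inebilizumab) | Placebo | Inebilizumab | Difference | Odds ratio |
|---|---|---|---|---|---|
| 0 / 0 | 0 / 0 | 65% | 86% | 21 points | 3.31 |
| 10% / 5% | 0 / 0 | 55% | 81% | 26 points | 3.49 |
| 5% / 5% | 0 / 0 | 60% | 81% | 21 points | 2.84 |
| 0 / 0 | 5% / 10% | 60% | 76% | 16 points | 2.11 |
| 10% / 5% | 5% / 10% | 50% | 71% | 21 points | 2.45 |

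One subject in an arm of 80 is 1/80 = 1.25 points. The last row shows the two changes cancelling on the difference while the odds ratio falls from 3.31 to 2.45.

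**Step 4: SAP 3.5.2.5.** The section title, the estimand variable, the endpoint lists in SAP Table 1 and SAP 3.5.2, and Protocol 9.5.2.2 all include untreated flares. Only the model sentence says treated, and it nearly repeats the corresponding sentence in SAP 3.5.2.1.

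**The case against.** The strongest reply is that little depends on this. The remission analysis is supplementary, the main remission definition matches the protocol, and no alpha-controlled test is touched. The retained condition matters only for completers who were treated for flare, not confirmed by the AC, and inactive at Week 52. Key secondary endpoint 3 and the time-to-first-treatment endpoint already give some view of treatment handling. All this is fair and limits the weight of the point. Neither of those endpoints, however, gives the remission proportion with treatment disregarded.

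An RI = 0 analysis is also a legitimate check on the investigator-determination route, and the SAP's revision history is too coarse to exclude a deliberate choice. That stands too: RI = 0 is not an error in itself. The errors are the label and the loss of the analysis the protocol planned.

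The shares in the illustration have no source in the documents, and they measure the SAP's version against the protocol's, not against the main composite. They show only that the shift can go either way.

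The 3.5.2.5 sentence is very probably a copying slip, given the contrary text around it. It still needs correcting, because it is the sentence that specifies the model.

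**Conclusion.** The point holds. Two governing documents prescribe different analyses under one name, and the SAP's version is neither treatment policy nor a change in treatment handling alone. The model sentence in SAP 3.5.2.5 contradicts its own estimand and the protocol.

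The size and direction cannot be determined from the documents. Under the assumed shares, the remission difference ranges from 16 to 26 points around a 21-point ceiling, and the odds ratio from 2.11 to 3.49 around 3.31. The scope is one supplementary analysis and one non-key secondary endpoint; the primary endpoint, the key secondary tests and the 160-subject design are unaffected. It should be settled before unblinding, so that the choice between the two versions is not made after results are known.

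**What to change.** 1. In SAP 3.5.2.2, define remission for the treatment-policy analysis as the protocol does: lack of evident disease activity at Week 52 by either route and no AC-determined flare during the RCP, regardless of treatment received. With no treatment condition, this one analysis serves both remission endpoints. SAP 3.5.2.3, which refers to two analyses but sets out only one, can point to it.
2. If the version with RI = 0 and no treatment for flare is wanted, keep it as a separately named composite sensitivity analysis.
3. In SAP 3.5.2.5, change the model sentence to count AC-determined flares, whether or not treated.

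The cost is two SAP sentences, the optional cross-reference, and one extra model run if the RI = 0 version is kept. No new data are needed.
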